4.4. Justification for Dose

4.4.1. Part A

Dose levels for Part A were selected on the basis of PK/PD predictions and preclinical data, which are summarised in Table 2. Please refer to the IB for further details.

A target mediated drug disposition model (TMDD) has been developed to characterise the aCCL17 PK and chemokine kinetics observed pre-clinically, and the model parameters were allometrically scaled to a 70 kg human [CP2015PK-002, 2016]. The estimated chemokine degradation rate (Kdeg=585.6/day) implies a chemokine half-life of approximately 2 minutes, considerably shorter than the 20-30 minutes expected. However, the estimated degradation rate (Kdeg) is derived by the assumption of low levels of serum CCL17 in equilibrium with extra cellular component, hence high accumulation of total (as observed in cynomolgus monkey) is explained by low CCL17 level and extremely high turnover. An alternative hypothesis is to assume a lower degradation rate and a much larger extra-cellular component outside plasma. An alternative model assuming a different chemokine degradation rate with a 10-minute half-life has been also developed. There are no differences in the estimated PK profiles for GSK3858279. The lower chemokine degradation rate also results in a longer return to baseline for the free chemokine profiles and sustained target engagement over a longer period. Predictions and safety margins are summarized in Table 2.

The 'Minimal Anticipated Biological Effect Level' (MABEL), as per Guideline on Strategies to Identify and Mitigate Risks for First-In-Human Clinical Trials with Investigational Medicinal Products [CHMP, 2017] was used to define the starting dose and is defined as the dose level predicted to result in a maximum inhibition in plasma in the 30-50% range. A dose of 0.1 mg/kg was designated the MABEL dose as the maximum predicted PD inhibition was 56%, according to human PK/PD predictions.

According to this model, the highest planned dose 10 mg/kg IV is expected to provide a maximum target engagement of 99% with half of this level being recovered after 9.5 days, and a return to baseline around three weeks post dose. Even at this highest simulated dose, high target engagement was not maintained over a 28-day period.

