
 • Reporting for tables, figures and formal statistical analyses: 
 ◦ Planned time relative to the first dosing will be used in figures, summaries and planned time relative to the last dosing will be used in statistical analyses and calculation of any derived parameters, unless otherwise stated. ◦ The impact of any major deviation from the planned assessment times and/or scheduled visit days on the analyses and interpretation of the results will be assessed as appropriate. • Reporting for Data Listings: 
 ◦ Planned and actual time relative to study drug dosing will be shown in listings (Refer to IDSL Statistical Principle 5.05.1). ◦ Unscheduled or unplanned readings will be presented within the subject's listings. 	
Unscheduled Visits	

 • Unscheduled visits will not be included in by-visit summary tables and figures. • All unscheduled visits will be included in listings and determination of worst-case values. 	
Descriptive Summary Statistics	
Continuous Data	Refer to IDSL Statistical Principle 6.06.1 – do not report 95% CI unless otherwise specified.
Categorical Data	N, n, frequency, %
Graphical Displays	

 • Refer to IDSL Statistical Principals 7.01 to 7.13. 	

[figure not shown]

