14.11.10.2. Part B

No.	Population	IDSL / Example Shell	Title	Programming Notes	Deliverable
Serum Target Engagement					

4.06	Safety	PD_T1	
Part B: Summary of Free & Total CCL17 in Serum Concentration-Time Data (pg/mL)
 
Please only present the median, min, max, sd (log), geometric mean and 95% CI back-transformed from the \log_e scale. Apply logit transformation for % reduction parameter. If % reduction ≤ 0, set to 0.1. If % reduction ≥ 100, set to 99.9. These imputations are needed for logit transformation. Use Student's t-distribution for CI.
 
Please only present the median, min, max, sd (log), geometric mean and 95% CI back-transformed from the \log_e scale. Apply logit transformation for % reduction parameter and present median, min, max, sd (logit), geometric mean and 95% CI back-transformed from the logit scale. If % reduction ≤ 0, set to 0.1. If % reduction ≥ 100, set to 99.9. These imputations are needed for logit transformation. Use Student's t-distribution for CI. Add the following footnotes: Note: Free CCL17 values below the LLOQ have been imputed to $\frac{1}{2}^*LLOQ$. Total CCL17 values below the LLOQ have been imputed to 0. Values equal to zero at baseline have been imputed to LLOQ whilst missing baseline values have been imputed to the median of the non-missing baseline values. Note: Free CCL17 and Total CCL17 exceeding the upper limit of quantification (ULOQ) have been excluded from the summary statistics (ULOQ Free CCL17: 3600 pg/mL, ULOQ Total CCL17: 50000 pg/mL). Note: If more than 30% of values have been imputed at any timepoint for a treatment group, then the standard deviation is not displayed. Note: Baseline is the mean of the Day -4 and Day 1 Pre-Dose assessments. Note: Percentage reduction and fold increase parameters were calculated using a model based post-hoc analysis. Note: Percentage reduction values ≤ 0 are imputed to be 0.1 and values ≥ 100 are imputed to be 99.9.
	Part B SAC
------	--------	-------	---	------------

No.	Population	IDSL / Example Shell	Title	Programming Notes	Deliverable
				Note: The percentage reduction parameter was logit transformed, summarised, and back-transformed using the logistic function to obtain the geometric summary statistics. The 95% CI of the geometric mean was calculated using Student's t distribution.	

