14.11.11. Pharmacodynamic Figures

14.11.11.1. Part A

No.	Population	IDSL / Example Shell	Title	Programming Notes	Deliverable
Serum Target Engagement					
4.01.	Safety	PK16	Part A: Individual Free & Total Serum CCL17 Concentration-Time Plots (Linear and Semi-log)	
One panel per dose group.
 
Add the following footnotes:
 
Note: Free CCL17 LLOQ = 2.93 pg/mL, ULOQ = 3600 pg/mL.
 
Note: Total CCL17 LLOQ = 13.11 pg/mL, ULOQ = 50000 pg/mL.
 
Note: The baseline value is presented at an actual relative time of 0 days.
 
Note: Any non-quantifiable (NQ) Free CCL17 concentration values have been set to $\frac{1}{2}^*\text{LLOQ}$.
 
Note: Any NQ Total CCL17 concentration values before the first measurable concentration have been set to 0 and have been included in the linear plot.
 
Note: Any single NQ values have been omitted.
 
Note: Any multiple mid-profile NQ concentrations of Free CCL17 and Total CCL17 have been set to $\frac{1}{2}^*\text{LLOQ}$ and 0, respectively, and the subsequent measurable concentrations have been retained.
 
Note: Percentage reduction values ≤ 0 are imputed to be 0.1 and values ≥ 100 are imputed to be 99.9
	Part A SAC

No.	Population	IDSL / Example Shell	Title	Programming Notes	Deliverable

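### The CCL17 summary tables suppress the SD when more than 30% of values are imputed but still print the 95% CI computed from that SD; for free CCL17 the interval is unreliable under heavy censoring and has zero width when every value is imputed

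*SAP*

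**What the plan says.** The programming notes for Table 4.06 (SAP 14.11.10.2, free and total CCL17 in serum, Part B) ask for a fixed set of statistics: "Please only present the median, min, max, sd (log), geometric mean and 95% CI back-transformed from the" log scale. They add "Use Student's t-distribution for CI". Table 4.01 does the same for Part A serum.

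The footnotes to these tables set three rules that matter here:

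- "Free CCL17 values below the LLOQ have been imputed to" half the LLOQ. The serum figure notes give the limits: "Free CCL17 LLOQ = 2.93 pg/mL, ULOQ = 3600 pg/mL".
- "Total CCL17 values below the LLOQ have been imputed to 0".
- "If more than 30% of values have been imputed at any timepoint for a treatment group, then the standard deviation is not displayed".

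The 30% footnote names only the SD. It also stands in Table 4.03 (blister fluid) and Table 4.04 (blister-to-serum ratio). The general default in SAP 14.5.2 is "do not report 95% CI unless otherwise specified", but these tables do specify a CI, so the default does not remove it.

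**The concern.** The footnote accepts that an SD is not fit to show once more than 30% of values are imputed. The 95% CI of the geometric mean is a direct multiple of that SD. Leaving the CI in the table therefore keeps the suppressed quantity in another form.

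For free CCL17 this matters more than usual, because all values below LLOQ are set to the same number. As the imputed share approaches 100%, the log-scale SD goes to zero and so does the CI. The narrowest intervals could then appear in the cells where the assay quantified least, and they would describe the imputation constant instead of the participants. Target engagement is a secondary objective in both parts, so a reader of the report may take such an interval as evidence of precision.

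**Working it through.** **Inputs.** From the SAP: free CCL17 LLOQ 2.93 pg/mL, imputed value 2.93/2 = 1.465 pg/mL, Student-t 95% CI. From Protocol 4.2: six active participants per Part A cohort, and about 50 in Part B at 1:1, so 25 per arm. Assumed, because the documents give no value: free CCL17 is lognormal with log-SD 0.5 to 0.8. The plan states no figure on this point to reproduce.

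**Formula.** With y = ln(concentration) and s its SD, the printed interval is exp[mean(y) ± t(0.975, n-1) × s/√n], where t = 2.571 for n = 6 and 2.064 for n = 25. The t instruction follows the notes on percentage reduction and could be read as applying only there. That makes no difference here, since the usual interval for a mean on the log scale rests on s either way.

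**Step 1: the hidden SD can be recovered.** s = ln(upper/lower) × √n / (2t). Example: n = 25, 8 values imputed, the rest spread evenly over 3 to 6 pg/mL (assumed). The CI is 2.464 to 3.891, and ln(3.891/2.464) × 5 / (2 × 2.064) = 0.553, which is the suppressed SD.

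**Step 2: how the interval behaves as more values are imputed** (n = 25, same assumed spread):

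| Imputed | SD (log) | Printed 95% CI, pg/mL |
|---|---|---|
| 8 of 25 | 0.553 | 2.46 to 3.89 |
| 13 of 25 | 0.581 | 1.95 to 3.16 |
| 20 of 25 | 0.460 | 1.51 to 2.20 |
| 24 of 25 | 0.143 | 1.42 to 1.60 |
| 25 of 25 | 0 | 1.465 to 1.465 |

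The fourth row (remaining value 3 pg/mL) can be checked by hand: s = [ln 3 - ln 1.465]/√25 = 0.717/5 = 0.143.

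**Step 3: chance of exactly zero width.** This is p^n, with p the true share below LLOQ. For n = 6: 0.8^6 = 26% and 0.9^6 = 53%. For n = 25: 0.9^25 = 7% and 0.95^25 = 28%.

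**Step 4: coverage and width by simulation** (20,000 runs per setting; values below 2.93 set to 1.465; coverage of the true geometric mean; log-SD 0.5 to 0.8; width relative to the same data without censoring):

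| Below LLOQ | Coverage, n = 25 | Relative width, n = 25 |
|---|---|---|
| 31% | 87-93% | 1.05-1.25 |
| 60% | about 72-94% | 0.85-1.09 |
| 80% | 44-94% | - |
| 90% | 0-91% | 0.39-0.54 |
| 95% | about 0% | 0.24-0.33 |

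For n = 6, relative width at 31% is about 1.06 to 1.27, and coverage is about 72-74% at 80% and 9-47% at 90%.

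The ranges are wide because coverage depends on where the true geometric mean, 2.93 × exp(-z × log-SD), lies relative to 1.465. At 90% below LLOQ (z = 1.282) it is 1.54 pg/mL for log-SD 0.5 and 1.05 for log-SD 0.8. At 95% (z = 1.645) it is already 1.29 for log-SD 0.5, below the imputed value. A larger log-SD is worse: at 1.2 and n = 25, coverage is about 27% at 70% below LLOQ and 0% at 90%.

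**Step 5: when would values fall below LLOQ?** A value does so when baseline < 2.93/(1 - reduction): 22.5 pg/mL at 87% reduction, 73 at 96%, 146.5 at 98% and 293 at 99%. No baseline CCL17 level is given, so the frequency cannot be derived.

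**The case against.** A reader might infer that the interval begins to shrink as soon as the 30% rule bites, or that it will collapse at the Part B dose. The documents do not support either reading.

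- **Shrinkage.** At 31% below LLOQ the printed CI is as wide as, or wider than, the uncensored one. Clear narrowing needs roughly 90% imputed, and zero width needs every value imputed.
- **The 99% prediction.** Protocol 4.4.1 says 10 mg/kg IV "is expected to provide a maximum target engagement of 99"%, but that is a single-dose Part A model prediction and the section adds that high engagement does not last 28 days. For 3 mg/kg SC, Table 2 of the protocol predicts 87%, where only baselines under 22.5 pg/mL would fall below LLOQ. Repeat dosing may do more, but no figure is visible, and Protocol 2.2 says there is no literature on circulating CCL17 in OA.
- **Scope.** Total CCL17 is set to 0, not to a constant with a logarithm, and is expected to rise on drug. Part B percentage reduction is model-based, so half-LLOQ imputation does not drive it unless the observed-data fallback in SAP 10.1.1.2.2 is used. No blister-fluid LLOQ is visible, and Table 4.04 is a ratio, so the figures above do not carry over to Tables 4.03 and 4.04.
- **Mitigation.** The tables already show median, minimum and maximum, and a footnote states the imputation. An all-imputed cell would show three identical values and no SD. Table shell PD_T1 and the sponsor's display standards are separate documents and could suppress the CI.

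These points limit the size and reach of the problem. They do not remove it: the SAP's own notes require the CI and suppress only the quantity it is built from.

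**Conclusion.** The rule is wrong as written, and the consequence is minor. For free CCL17 concentrations in serum (Tables 4.01 and 4.06), the SAP prints a 95% CI that is unreliable when most values are imputed and has zero width when all are. Tables 4.03 and 4.04 carry the same inconsistent footnote, without a size that can be given. The mechanism and the all-imputed case follow from the SAP text alone. The coverage figures rest on lognormal data with an assumed log-SD of 0.5 to 0.8. The frequency of heavy censoring remains unknown. The 30% footnote, and the fallback for a high level of non-reportable data in SAP 10.1.1.2.2, show that the sponsor allows for it.

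The effect is confined to descriptive tables for a secondary objective. The primary pain analysis is untouched. The setting of total CCL17 to 0 before a log-scale summary is a separate matter.

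**What to change.** Extend the existing 30% footnote so that it also suppresses the 95% CI of free CCL17 concentrations, and print n (%) below LLOQ beside the median, minimum and maximum already shown. If an interval is wanted in heavily censored cells, estimate it from a left-censored lognormal likelihood and label it so.

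The cost is one SAP note and a matching change to the table shell. The downside is that some cells lose their CI: from 2 of 6 imputed in a Part A active cohort (33%) and from 8 of 25 in a Part B arm (32%). That includes cells with moderate imputation where coverage is still acceptable; for n = 6 it is about 94% at 31% below LLOQ and 87-92% at 60%.

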	Non-Clinical In the nonclinical studies a significant number of monkeys treated with GSK3858279 had confirmed ADA, but mostly the presence of ADA did not affect the systemic exposure or PK parameters for GSK3858279; however, there was no impact on clinical observations apart from the animal which had findings consistent with an infusion-related reaction and on the chronic toxicology study, vascular changes consistent with ICD were seen (mentioned above). In general, the incidence and titre of ADA in nonclinical studies are not predictive of human.	be investigated following unexplained dipstick proteinuria or haematuria.
	Clinical The FTIH study in healthy participants showed there was low incidence of ADA, low titre, no pattern of increasing incidence of ADAs following single ascending dose (SAD) of GSK3858279 (or placebo) and no apparent difference between 3 mg/kg IV vs. 3 mg/kg SC.	
Vaccination reactions	There is a theoretical risk that GSK3858279 could decrease an individual's immune response to vaccines administered while on therapy or to allow symptoms to develop following the administration of live vaccines. Monkeys dosed with GSK3858279 for 13 weeks did not demonstrate modulation of the immune system as assessed by T-cell Dependent Antibody Response (TDAR), an assessment of humoral immunity, or of peripheral blood lymphocyte populations as assessed by flow cytometry.	Participant selection and non-permitted medications: Attenuated live should not be administered to participants from 30 days prior to the first dose of study drug and for five half-lives after dosing. If indicated, non-live vaccines (e.g. inactivated influenza vaccines) may be administered whilst receiving study drug based on an assessment of the benefit:risk (e.g. risk of decreased responsiveness). See Section 5.2
Cardiac risks	Non-Clinical In the 4-week study, review of the heart data (Electrocardiogram [ECG], blood pressure, heart rate, organ weights and histopathology), in monkeys at doses up to 100 mg/kg/week IV	Participant Exclusion Participants with a history of cardiac disease or cardiac abnormalities that in the opinion of the investigator would compromise cardiac safety will be excluded from the study.

Potential Risk of Clinical Significance	Summary of Data/Rationale for Risk	Mitigation Strategy

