8.5. Immunogenicity Assessments

Serum samples will be collected from all treated participants at pre-dose and various time points post-dosing. The washout samples will be collected at the follow-up visit to minimise interference of circulating drug in the antibody assessments, see SoA (Section 1.3.5). Testing will be performed using the typical tiered approach involving screening, confirmation and titration assays [EMEA, 2017; FDA, 2014], performed by IVIVT, GSK. If sera contain potential anti-GSK3858279 antibodies, they will be confirmed by immune-competition using excess drug, followed by a titration assay.

For each participant, immunogenicity results, including the incidence and titres, will be reported.

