10.3. Immunogenicity

10.3.1. Summary Measure

The number and percentage of confirmed positive samples in each treatment group will be presented at each time assessed. Only binding antibody detection is collected in this study. Neutralising antibody detection is not collected.

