ECG					
2.33.	Safety	EG1	Part B: Summary of ECG Findings		IA3, Part B SAC
2.34.	Safety	EG10	Part B: Summary of Maximum QTc Values Post-Baseline Relative to Baseline by Category	Use QTcB and QTcF intervals	IA3, Part B SAC
2.35.	Safety	EG2	Part B: Summary of Change from Baseline in ECG Values by Visit	Use QTcB and QTcF intervals	IA3, Part B SAC

No.	Population	IDSL / Example Shell	Title	Programming Notes	Deliverable
2.36.	Safety	EG11	Part B: Summary of Maximum Increase in QTc Values Post-Baseline Relative to Baseline by Category	Use QTcB and QTcF intervals	IA3, Part B SAC
Immunogenicity					
2.37.	Safety	AE1CP	Part B: Summary of Treatment-Emergent Adverse Events by Highest Post-Baseline ADA Result	Split table by Positive/ Negative ADA status	Part B SAC
Injection Site Reactions					
2.38.	Safety	SAFE_T1	Part B: Summary of Injection Site Reactions as per specified AE Term list	Safety to provide list of HLT / Preferred Terms. Add a footnote explaining that this table was created using a pre-specified subset of MedDra AE Terms	Part B SAC
2.39.	Safety	ESI1	Part B: Summary of Characteristics of Injection Site Reactions as per specified AE Term list	Safety to provide list of HLT / Preferred Terms. Add a footnote explaining that this table was created using a pre-specified subset of MedDra AE Terms	Part B SAC

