4.07.	Safety	PD_T2	Part B: Summary of Model-Derived Free and Total CCL17 in Serum Target Engagement Parameters (non- transformed and log- transformed)	
Please only present the median, min, max, sd (log), geometric mean and 95% CI back-transformed from the \log_e scale.
 
Please note that tmin and tmax should not be \log_e-transformed and 95% CI should not be presented.
 
Apply logit transformation for % reduction and maximum % reduction parameters.
 
If % reduction ≤ 0, set to 0.1.
 
If % reduction ≥ 100, set to 99.9.
 
These imputations are needed for logit transformation.
 
Use Student's t-distribution for CI.
 
Add the following footnotes:
 
Note: All Target Engagement parameters were calculated using a model based post-hoc analysis.
 
Note: Percentage reduction values ≤ 0 are imputed to be 0.1 and values ≥ 100 are imputed to be 99.9.
 
Note: The percentage reduction and maximum percentage reduction parameters were logit transformed, summarised, and back-transformed using the logistic function to obtain the geometric summary statistics. The 95% CI of the geometric mean was calculated using Student's t distribution.
	IA3, Part B SAC
Immunogenicity					
4.08.	Safety	IMM1	Part B: Summary of Immunogenicity	Add extra row for Part B SAC - "Highest post-baseline" result. This would be #participants with at least one post-baseline positive result / # participants with at least one post baseline sample.	IA3, Part B SAC

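### Two Part B displays, the added Highest post-baseline row of Table 4.08 and the ADA split of Table 2.37, pool participants who were antibody-positive before dosing with those who became positive afterwards

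*SAP*

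**What the plan says.** SAP 10.3.1 sets the general summary for immunogenicity: "The number and percentage of confirmed positive samples in each treatment group will be presented at each time assessed". This is a count by visit and arm.

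SAP 14.11.10.2 adds one row to Table 4.08 for the final Part B delivery. The row is labelled as the highest post-baseline result and defined so: "This would be #participants with at least one post-baseline positive result / # participants with at least one post baseline sample". The pre-dose result enters neither numerator nor denominator.

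SAP 14.11.7.2 lists Table 2.37, "Part B: Summary of Treatment-Emergent Adverse Events by Highest Post-Baseline ADA Result", with the programming note "Split table by Positive/ Negative ADA status".

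Protocol 8.5 shows that the data for a baseline comparison exist. On sampling: "Serum samples will be collected from all treated participants at pre-dose and various time points post-dosing". On reporting: "For each participant, immunogenicity results, including the incidence and titres, will be reported".

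The clinical ADA experience in the documents comes from Part A. Protocol 2.3.1 reports "low incidence of ADA, low titre, no pattern of increasing incidence of ADAs following single ascending dose (SAD) of GSK3858279 (or placebo". It gives no rate of pre-dose positivity.

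**The concern.** A pre-dose positive result cannot be a response to the study drug. If such a participant stays positive, the added row counts them exactly like someone who was negative before dosing and developed antibodies. The row is the only participant-level ADA rate visible in the plan, so readers will tend to take it as the incidence on treatment. Table 2.37 is the only visible display that relates adverse events to ADA status, and its positive column would mix the same two groups. If ADA formed on treatment do carry a risk, adding participants with unchanged pre-existing reactivity would probably dilute the contrast, although that direction is not certain.

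Immunogenicity is part of the stated purpose of Part B, and protocol 2.3.1 links ADA to hypersensitivity and immune complex disease. With few true converters, one or two pre-existing reactors could make up much of the positive group.

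**Working it through.** The plan states no ADA rate, so there is no figure to reproduce. The check is of the definition, followed by an illustration with assumed counts.

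**1. Is a baseline-adjusted definition given elsewhere?** SAP 10.3.1 counts confirmed positives by time. SAP 14.6.5 deals only with anonymising participants for the safety reviews. Protocol 8.5 describes the screening, confirmation and titration assays. None of these defines treatment-induced, treatment-boosted or treatment-emergent ADA.

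**2. How does the stated rule classify each pattern?**

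| Pre-dose | Any post-baseline positive | Class under the rule |
|---|---|---|
| Negative | No | Negative |
| Negative | Yes | Positive |
| Positive | No | Negative |
| Positive | Yes | Positive |

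The second and fourth patterns fall into one class, whether or not the titre rose.

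**3. Is this how the SAP treats other safety data?** The Part B worst-case tables for vital signs, haematology, chemistry and urinalysis, and the maximum QTc tables, are set relative to baseline. In Table 2.37 the adverse events must be treatment-emergent, but the ADA status that groups them need not be.

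**4. What could it do to the row?** Protocol 9.2.1 plans about 50 participants at 1:1, so 50 / 2 = 25 per arm. Let b be pre-dose positives who stay positive without a titre rise, and t be converters. Both are assumed. The row is (b + t) / 25, and the treatment-emergent rate on the same denominator is t / 25. With t = 2:

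| b | Planned row | Treatment-emergent | Pre-existing share of the positive group, b / (b + t) |
|---|---|---|---|
| 0 | 2/25 = 8% | 2/25 = 8% | 0% |
| 1 | 3/25 = 12% | 8% | 1/3 = 33% |
| 2 | 4/25 = 16% | 8% | 2/4 = 50% |
| 3 | 5/25 = 20% | 8% | 3/5 = 60% |

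Letting b and t each run from 1 to 3, the excess is b / 25, or 4 to 12 percentage points. The pre-existing share then runs from 1/4 = 25% to 3/4 = 75%.

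**5. How likely is at least one pre-dose positive?** For an assumed prevalence p, the chance among n participants is 1 − (1 − p)^n.

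| p | n = 25 | n = 50 |
|---|---|---|
| 1% | 22% | 40% |
| 2% | 40% | 64% |
| 5% | 72% | 92% |
| 10% | 93% | 99.5% |

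The documents do not say which of these prevalences applies.

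**The case against.** Much of the case on the other side stands.

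- *Scope.* The note governs one added row. The rest of Table 4.08 is by time and treatment group, and pre-dose samples are taken from everyone treated, so pre-dose positivity by arm should appear there. Listing 84 allows a participant-level trace at the final analysis; its restriction to positives applies to IA3 only. A reader might infer that the whole Part B ADA summary ignores baseline. The documents do not support that.
- *Labels.* The row and Table 2.37 both say post-baseline. A reader might infer that the SAP presents pre-existing reactivity as drug-induced ADA. It makes no such claim; what is missing is a category.
- *Placebo.* Background reactivity should appear in both randomised arms, so the difference between arms in the new row largely allows for it in expectation. That holds for the row. It does not help Table 2.37, where individuals are grouped by status.
- *Safety meaning.* The stated risk is that ADA are present, so grouping by any post-baseline positivity is defensible. Splitting Table 2.37 on treatment-emergent status alone, in two columns, would move persistent positives into the negative group. That would be a poor replacement.
- *Evidence on size.* Part A showed low incidence and low titre, which points towards a small effect. Protocol 8.5 also recognises that circulating drug interferes with the assay, so not every pre-dose positive need test positive later.
- *Consequence.* Both displays are descriptive. The row and Table 2.37 come only with the final Part B delivery. No visible interim decision, test or stopping rule uses them.
- *Unseen shell.* The IMM1 shell for Table 4.08 is not in the documents and may already hold baseline or titre rows.

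What survives is narrow. By-time group counts and a listing do not separate the two kinds of positive in the participant-level rate, and nothing in Table 2.37 as specified does so.

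**Conclusion.** The point holds in a limited form. The Highest post-baseline row of Table 4.08 and the positive/negative split of Table 2.37 do not condition on the pre-dose ADA result, so persistent pre-dose positives and post-dose converters share one class.

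The size cannot be read from the documents. The range of 8% to 20% against 8% rests on 25 participants, 2 converters, and 0 to 3 pre-dose positives who all stay positive without a titre rise. A reader might infer from the upper figures that the trial will overstate incidence by a known factor, here 1.5 to 2.5 times with 1 to 3 pre-dose positives (12/8 to 20/8). That ratio comes wholly from the assumed counts, and with no pre-dose positives it is 1. No primary endpoint visible in the plan is affected. This is a cheap improvement to two descriptive displays.

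**What to change.** Before unblinding, the SAP should:

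- keep the Highest post-baseline row of Table 4.08 as it is;
- add a row for participants positive at baseline;
- add a row for treatment-emergent ADA, meaning a negative baseline followed by a confirmed post-baseline positive, or a positive baseline with a titre rise above a threshold. The documents give no threshold, so the sponsor has to set it in advance. The row should also state its denominator: all participants with a post-baseline sample, or baseline-negatives only;
- split Table 2.37 into treatment-emergent positive, baseline-positive without a titre rise, and negative, so that persistent positives are not placed in the negative column.

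Pre-dose samples and titres are already collected, so the cost is one definition and two programming notes. The downside is a few more rows and a third category in Table 2.37 that may be very small or empty.
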